12. APPENDICES

12.1. Appendix I - Abbreviations

Abbreviations

AE	Adverse Event
AOB	Area over baseline
CD	Compact Disc
CRF	Case Report Form
EDC	Electronic Data Capture
GCP	Good Clinical Practice
GSKCH	GlaxoSmithKline Consumer Healthcare
Hr	Hour
ICH	International Conference on Harmonization of Technical Requirements
	for Registration of Pharmaceuticals for Human Use
IEC	Independent Ethics Committee
IRB	Institutional Review Board
ITT	Intention to Treat
OST	Oral soft tissue
PII	Personally Identifiable Information
PP	Per Protocol
PRO	Patient Reported Outcome
PVA	Polyvinyl acetate
SAE	Serious Adverse Event
US	United States of America

Trademark Information

Trademarks of the GlaxoSmithKline group of companies:
POLIGRIP

Document Name	Project CCI protocol		
Туре	Version	Document Identifier	Effective Date
eldo clinical doc	5.0; Most-Recent; Effective; CURRENT	090032d580cfe581	23-Feb-2017 14:35:47
Reason For Issue	Auto Issue		

12.2. Appendix II - Product Ooze Questionnaire

Please note that this questionnaire is only completed for subjects on treatment visits when they have a denture adhesive applied and NOT on the no adhesive treatment visit.

Question 1 to be completed by the subject immediately after the 0.5 hour bite force reading.

Please mark/ tick only **ONE** response per question.

1. How long after inserting your denture did you experience denture adhesive OOZING out of your UPPER DENTURE?

Immediately	Less than approximately 10 minutes		Approximately 20 to 30 minutes	No ooze experienced
1	2	3	4	5

Document Name	Project CCI protocol		
Туре	Version	Document Identifier	Effective Date
eldo clinical doc	5.0; Most-Recent; Effective; CURRENT	090032d580cfe581	23-Feb-2017 14:35:47
Reason For Issue	Auto Issue		

12.3. Appendix III - Sensory Questionnaire

Please note that this questionnaire is only completed for subjects on treatment visits when they have a denture adhesive applied and NOT on the no adhesive treatment visit.

To be completed by the subject immediately following the last (12 hr) bite force measure (whilst upper denture still retained in the mouth). Questions relate to the UPPER DENTURE only.

Please mark/ tick only **ONE** response per question.

1. How would you rate your OVERALL OPINION of the denture adhesive?

Dislike extremely	Dislike moderately	Dislike slightly	Neither like nor dislike	Like slightly	Like moderately	Like extremely
1	2	3	4	5	6	7

2. How much did you LIKE/ DISLIKE the TASTE of the denture adhesive?

Dislike extremely	Dislike moderately	Dislike slightky	Neither like nor dislike	Like slightly	Like moderately	Like extremely
1	2	3	4	5	6	7

Document Name	Project CCI protocol		
Туре	Version	Document Identifier	Effective Date
eldo clinical doc	5.0; Most-Recent; Effective; CURRENT	090032d580cfe581	23-Feb-2017 14:35:47
Reason For Issue	Auto Issue		

3.	How would you describe the STRENGTH of the TASTE of the denture
	adhesive?

No flavour at all	Barely detectable	Weak	Moderate	Strong	Very strong	Strongest flavour imaginable
1	2	3	4	5	6	7

4. How much did you LIKE/ DISLIKE the FEEL of the adhesive in the mouth?

Dislike extremely	Dislike very much	Dislike moderately	Neither like nor dislike	Like moderately	Like very much	Like extremely
1	2	3	4	5	6	7

5. How would you describe the TEXTURE of the denture adhesive?

	Not at all	Slightly	Moderately	Very	Extremely
Smooth					
Oily					

Document Name	Project CCI protocol	et CCI protocol			
Туре	Version	Document Identifier	Effective Date		
eldo clinical doc	5.0; Most-Recent; Effective; CURRENT	090032d580cfe581	23-Feb-2017 14:35:47		
Reason For Issue	Auto Issue				

Gritty					
	1	2	3	4	5

For the following question subjects to be given a tube of the test product and asked to squeeze the adhesive on to a piece of paper as per the strips that appear on the product application

6. How EASY was it to SQUEEZE OUT the adhesive from the tube?

Not at all easy	Slightly easy	Moderately easy	Very easy	Extremely easy
1	2	3	4	5

Document Name	Project CCI protocol	protocol			
Туре	Version	Document Identifier	Effective Date		
eldo clinical doc	5.0; Most-Recent; Effective; CURRENT	090032d580cfe581	23-Feb-2017 14:35:47		
Reason For Issue	Auto Issue				

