The Area Over Baseline (AOB) over 12 hours for the incisal bite force (lbs) (denoted by AOB₀₋₁₂) is the primary efficacy variable. To calculate this variable first the Area Under the Curve (AUC) is calculated from 0 to 12 hours (AUC₀₋₁₂) using the trapezoid method. AOB₀₋₁₂ will be calculated as (AUC₀₋₁₂)/12 minus baseline bite force (lbs). An Analysis of Covariance (ANCOVA) model will be used to analyse AOB₀₋₁₂, with treatment and period as fixed effects; the covariates in this model are the subject level baseline and period level baseline minus subject level baseline. Subject will be included as a random effect.

If statistical significance is not obtained for at least one test adhesive vs no adhesive then the study validity will be evaluated by comparing Super Poligrip® Free vs no adhesive.

AOB for 0.5, 1, 3, 6 and 9 hours will be defined and analysed in a similar manner as AOB_{0-12} .

Subject questionnaire and denture adhesive weight data will be summarized using summary statistics only and no formal statistical analyses will be performed.

Document Name	Project CCI protocol		
Туре	Version	Document Identifier	Effective Date
eldo clinical doc	5.0; Most-Recent; Effective; CURRENT	090032d580cfe581	23-Feb-2017 14:35:47
Reason For Issue	Auto Issue		

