6.2.4. Subject Questionnaires

These questionnaires will only be completed by the subjects during treatment visits where subjects are assigned to adhesive.

A questionnaire pertaining to product ooze will be completed by the subjects immediately after the 0.5 hrs bite force measurement (Appendix II). Furthermore, a questionnaire regarding sensory attributes around flavour and texture will be completed immediately after completion of the 12 hrs bite force measurement whilst the upper denture is still retained in the mouth (Appendix III). Completion of this questionnaire will also involve the subject extruding some denture adhesive onto paper prior to answering the question regarding ease of product extrusion (question 6; Appendix III). A third and final denture removal questionnaire will be completed immediately following the 12 hrs bite force measurement, following completion of the sensory questionnaire and removal of the upper denture from the mouth by the subject (Appendix IV). This final "denture removal questionnaire" (Appendix IV) must be reviewed by Study Staff immediately following completion whilst the subject is still present, in order to ensure that any potential AEs that may be included in the free text (question 3; Appendix IV) are investigated by Study Staff and captured in the eCRF.

Document Name	Project CCI protocol		
Туре	Version	Document Identifier	Effective Date
eldo clinical doc	5.0; Most-Recent; Effective; CURRENT	090032d580cfe581	23-Feb-2017 14:35:47
Reason For Issue	Auto Issue		

All questionnaires will be completed by the subjects according to the study schedule (i.e. when undertaking the treatment, but not the no-treatment negative control study arms) in a quiet environment without external influence. Subjects will not be issued a questionnaire when completing the 'no adhesive' negative control treatment arm. The study Investigator(s) (in particular all site study staff involved in the collection of bite force and OST data) will remain blinded to the distribution and completion of all questionnaires. All questionnaire data will be captured in the eCRF, and will be monitored on site in order to ensure that all patient reported outcomes are captured in the database, paying particular attention to the free text about denture adhesive likes & dislikes (question 2; Appendix IV).

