post bite force phase	12 hours' use

3 Study Design

Overall Design

This single centre, randomized, crossover, proof-of-principle study will be a randomized four treatment, examiner blind [to the examiner performing the bite force & oral soft tissue (OST) examinations] design in subjects with well made and moderately well-fitting maxillary complete dentures. Informed consent will be obtained from participants before the implementation of any study procedure.

At the Screening Visit, subjects will be screened for eligibility and ability to perform the bite force manoeuvre according to stated inclusion/exclusion criteria. On the test day visit, subjects will report to the study site without adhesive placed in their dentures. Dentures will be removed and cleaned. An OST examination will be performed before the lower denture (if applicable) is secured using Super Poligrip[®] Flavour Free denture adhesive, whilst the upper denture is removed, and the pretreatment baseline incisal bite force measurements will be obtained (both practice bites and qualifying test bite). To maintain blinding, subjects must not disclose to the examiner if they are wearing adhesive or no adhesive. Subjects meeting all the inclusion criteria with no exclusions will then be randomized at Visit 2.

On each test day (Visits 2-5) subjects will undergo an OST examination and have their dentures cleaned. Denture adhesive treatment (or no treatment as per the randomization schedule) will then be applied by a member of study staff (ideally the same member of staff throughout the study) as per the application instructions, and the dentures worn by the subject. Incisal bite force measurements will be made at 0.5, 1, 3, 6, 9 and 12 hours after the dentures are placed in the mouth. After 0.5 hours assessment the subjects will be asked to complete questions about product ooze (Appendix II). The questions will be completed by the subjects themselves and these responses will then be given to study site staff to transfer to the eCRF.

Immediately following the last (12 hour) incisal bite force measurement, subjects will be asked to complete a short questionnaire relating to the after-taste and texture of the

Document Name	Statistical Analysis Plan for Study 206233.docx		
Туре	Version	Document Identifier	Effective Date
eldo clinical doc	1.0; CURRENT; Most-Recent; Effective	090032d580d17d34	27-Mar-2017 09:54:18
Reason For Issue	Auto Issue		

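### Appendix III allows one response per question, but Question 5 (texture) is a single question with three rows to rate; a subject who takes the instruction literally leaves two of the three texture scores blank.

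*Protocol*

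**What the plan says.** The instruction at the head of Protocol Appendix III (Section 12.3) applies to the whole questionnaire: "Please mark/ tick only ONE response per question". Questions 1 to 4 and Question 6 each have one response scale, so the rule fits them. Question 5 asks "How would you describe the TEXTURE of the denture adhesive" and is laid out as a grid. Its rows are Smooth, Oily and Gritty, and its five columns run from Not at all to Extremely, coded 1 to 5.

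The form is used at the three adhesive visits and not at the no-adhesive visit. Protocol Section 6.2.4 (Subject Questionnaires) says: "These questionnaires will only be completed by the subjects during treatment visits where subjects are assigned to adhesive". The SAP (Section 3, Study Design) repeats that after the 12-hour bite "subjects will be asked to complete a short questionnaire relating to the after-taste and texture of the" adhesive, and adds nothing on how Question 5 is to be marked.

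Texture is named in one of the objectives listed as Other (Protocol Section 2; SAP Section 2). The planned use of the data is descriptive. The Protocol Synopsis, under Statistical Methods, says: "Subject questionnaire and denture adhesive weight data will be summarized using summary statistics only and no formal statistical analyses will be performed". Protocol Section 9.3.4 and SAP Section 8.3 agree.

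**The concern.** Read literally, the rule and the grid cannot both be satisfied: one mark is allowed and three are needed. The subject completes the form without outside influence at the 12-hour point, with the upper denture still in the mouth. A rating left blank then is hard to recover faithfully through a later query.

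The stated checks do not clearly close the gap:

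- The staff review while the subject is still present (Section 6.2.4) is specified for the denture removal questionnaire in Appendix IV, and its purpose is to find adverse events.
- The review of patient-reported source data in Section 8.4 also looks for adverse events.
- The broader safeguard in Section 6.2.4, "All questionnaire data will be captured in the eCRF, and will be monitored on site in order to ensure that all patient reported outcomes" reach the database, ensures that what was marked is captured. It does not say that three marks are expected.
- The SAP has no rule for a Question 5 returned with one mark, or with three.

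Question 5 is the only item that asks the subject to describe texture; Question 4 asks how much the feel was liked. If some subjects tick once and others three times, the Smooth, Oily and Gritty counts for an adhesive would rest on different numbers of subjects, and no rule explains the blanks.

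**Working it through.** The plan gives no figure to reproduce here. The check is a reading of the form and a count.

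**Inputs**
- Rows in Question 5: 3 (Protocol Appendix III).
- Marks allowed per numbered question: 1 (Appendix III instruction).
- Visits at which the form is used: 3 of the 4 periods (Protocol Section 6.2.4, Subject Questionnaires).
- Completers planned: about 18; randomized: about 21 (Protocol Section 9.1; SAP Section 4).
- Share of subjects who read the instruction literally: p. The documents do not give it, so it is an assumption and is shown as a range.

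**Per subject**
- Blank scores per visit under the literal reading: 3 − 1 = 2 of 3.
- Over three adhesive visits: 2 × 3 = 6 of 9 blank, leaving 3.

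**Across 18 completers**
- All rows rated: 3 rows × 3 visits × 18 = 162 ratings.
- One mark per form: 1 × 3 × 18 = 54 ratings, and 54/162 = 33%.
- In general, with a share p reading literally at every visit: ratings = 162 − (162 − 54)p = 162 − 108p.

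| Assumed p | Texture ratings | Share of 162 |
|---|---|---|
| 0% | 162 | 100% |
| 10% | 162 − 10.8 ≈ 151 | 93% |
| 25% | 162 − 27 = 135 | 83% |
| 50% | 162 − 54 = 108 | 67% |
| 100% | 162 − 108 = 54 | 33% |

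**Sensitivity to the population.** SAP Appendix 2 lists Table 9.3.4 for all randomised subjects. If all 21 attended every adhesive visit, the range would be 1 × 3 × 21 = 63 to 3 × 3 × 21 = 189. The proportions do not change.

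**Search for an exception.** The appendix itself, Protocol Section 6.2.4, the footnotes to the Schedule of Events and the SAP do not say that Question 5 takes one response per row.

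**The case against.** The strongest reply is that nobody would read the form this way. The same instruction heads Appendices II, III and IV. In Appendix IV it also covers a free-text item with separate boxes for likes and dislikes, so it was plainly not tailored to each item. Its evident purpose is to prevent two ticks on one scale. A grid of three labelled rows and five intensity columns is ordinarily answered row by row. Staff are at hand when the form is completed, since the subject is given a tube for Question 6. Freedom from external influence need not forbid explaining the layout. Programmed edit checks run at data entry (Protocol Section 8.3.1), and the eCRF, which is not among the documents, may already require three fields.

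Much of this stands. It makes widespread literal reading unlikely, and it sets the priority. It does not remove the conflict on the printed form, and none of these safeguards is stated to cover Question 5.

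Several stronger inferences are tempting and are not supported:

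- **That two thirds of the texture data will be lost.** The 33% figure needs every subject to tick once at every visit. It is the worst case, not an expected loss.
- **That a within-subject comparison is destroyed.** No paired texture analysis is planned. The Table 9.3.4 template gives counts and percentages by treatment.
- **That subjects would rate only the most striking attribute, so that missingness depends on the rating.** This is conceivable, but nothing in the documents bears on it.
- **That the SAP will drop or merge the three rows.** The Table 9.3.4 template is an abbreviated shell showing only the first question of each questionnaire. The absence of Question 5 from it proves nothing.

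**Conclusion.** The form contradicts itself, and nothing in the protocol or SAP resolves it. A subject who obeys the instruction literally leaves 2 of 3 texture scores blank at each adhesive visit. With 18 completers the yield lies between 54 and 162 ratings. The position within that range depends on an unknown share of literal readers. The expectation that it falls nearer the upper end is a judgement from the grid layout, not a figure from the documents.

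The reach is narrow: descriptive summaries for one of the objectives classed as Other. A reader should not infer any effect on the primary or secondary bite force comparisons, the success criterion or the safety analyses, because none of them uses this questionnaire. The point is correct but of low priority. It is worth making because the correction is very small and a blank 12-hour rating is hard to recover.

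**What to change.** Change the Appendix III instruction so that it asks for one response per question and, for Question 5, one response in each row (Smooth, Oily, Gritty). Renumbering the rows 5a, 5b and 5c would do the same job and leave the general instruction true as printed. Have the eCRF expect three entries for Question 5, so that a blank row is noticed at entry. When the Table 9.3.4 shell is completed, give each row its own block with its own count of responders.

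The cost is a minor amendment to a subject-facing form, with IRB submission as local requirements dictate, and an eCRF field check if one is not already there. No visits, procedures or analyses are added.

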12.4. Appendix IV - Denture Removal Questionnaire

Please note that this questionnaire is only completed for subjects on treatment visits when they have a denture adhesive applied and NOT on the no adhesive treatment visit.

To be completed by the subject immediately after denture removal.

Please mark/ tick only **ONE** response per question.

1. How EASY was it to REMOVE the denture from the	he mouth	ıth
---	----------	-----

Not at all easy	Slightly easy	Moderately easy	Very easy	Extremely easy
1	2	3	4	5

2. How EASY was it to REMOVE ANY RESIDUAL DENTURE ADHESIVE from the mouth?

Not at all easy	Slightly easy	Moderately easy	Very easy	Extremely easy
1	2	3	4	5

3. Please describe below what you LIKED or DISLIKED about the denture adhesive.

LIKED	

Document Name	Project CCI protocol				
Туре	Version	Document Identifier	Effective Date		
eldo clinical doc	5.0; Most-Recent; Effective; CURRENT	090032d580cfe581	23-Feb-2017 14:35:47		
Reason For Issue	Auto Issue				

DISLIKED	
DISLIKED	

Document Name	Project CCI protocol				
Туре	Version	Document Identifier	Effective Date		
eldo clinical doc	5.0; Most-Recent; Effective; CURRENT	090032d580cfe581	23-Feb-2017 14:35:47		
Reason For Issue	Auto Issue				

12.5. Appendix V – Denture Adhesive Application Instructions (Super Poligrip®)

Super Poligrip® (Reference Product)

APPLYING TO UPPER (AND WHERE NECESSARY LOWER) DENTURES:

- 1. Clean and dry dentures.
- 2. Pre-dispense sufficient denture adhesive to remove any potential separation in order to ensure product uniformity prior to application to the denture.
- Apply product in strips, not too close to the denture edges (3 strips should be applied to the upper denture and 2 on the lower denture where necessary) as indicated in the images.
- 4. Maxillary dentures should be weighed before and after adhesive application to ensure correct dose applied (1±0.05 gram).

Document Name	Project CC protocol		
Туре	Version	Document Identifier	Effective Date
eldo clinical doc	5.0; Most-Recent; Effective; CURRENT	090032d580cfe581	23-Feb-2017 14:35:47
Reason For Issue	Auto Issue		

- 5. Where necessary, denture adhesive application to the lower denture should be sufficient to fully retain the lower denture in order to ensure accuracy of maxillary denture dislodgement bite force measures; please note that the lower denture images are for illustrative purposes only.
- 6. Have subjects rinse their mouth with water before inserting dentures.
- 7. Have subjects press dentures into place, hold firmly, and bite down for a few seconds to secure hold.

Document Name	Project CC protocol		
Туре	Version	Document Identifier	Effective Date
eldo clinical doc	5.0; Most-Recent; Effective; CURRENT	090032d580cfe581	23-Feb-2017 14:35:47
Reason For Issue	Auto Issue		

12.6. Appendix VI – Denture Adhesive Application Instructions (Experimental Denture Adhesives with a thin nozzle)

Experimental Denture Adhesives with Precision Applicator (Test Products)

APPLYING TO UPPER DENTURES:

- 1. Clean and dry upper dentures.
- 2. Pre-dispense sufficient denture adhesive to remove any potential separation in order to ensure product uniformity prior to application to the denture.
- 3. Apply product in long continuous strips as shown in the image, not too close to the denture edge (3 strips should be applied to the upper denture).
- 4. Maxillary dentures should be weighed before and after adhesive application to ensure correct dose applied (1±0.05 gram).
- 5. Have subjects rinse their mouth with water before inserting the upper denture
- 6. Have subjects press upper denture into place, hold firmly, and bite down for a few seconds to secure hold

Document Name	Project Colorotocol		

PP	Per Protocol
PT	Preferred Term
SAE	Serious Adverse Event
SAP	Statistical Analysis Plan
SD	Standard Deviation
SOC	System Organ Class

Document Name	Statistical Analysis Plan for Study 206233.docx		
Туре	Version	Document Identifier	Effective Date
eldo clinical doc	1.0; CURRENT; Most-Recent; Effective	090032d580d17d34	27-Mar-2017 09:54:18
Reason For Issue	Auto Issue		

1 Introduction

This document describes the statistical methods and data presentations to be used in the summary and analysis of the final data from Protocol 206233. This Statistical Analysis Plan (SAP) will be approved before unblinding and database freeze.

SAS version 9.4 will be used for the analyses. All statistical analyses mentioned in this SAP will be performed by inVentiv Health Clinical.

2 Objectives

Objectives	Endpoints
Primary	_
To compare incisal bite force for test adhesive 1 versus no adhesive after 12 hours.	AOB at 12 hours.
To compare incisal bite force for test adhesive 2 versus no adhesive after 12 hours.	AOB at 12 hours.
Secondary	
To compare incisal bite force for test adhesive 1 versus Super Poligrip® Free after 12 hours.	AOB at 12 hours.
To compare incisal bite force for test adhesive 2 versus Super Poligrip® Free after 12 hours.	AOB at 12 hours.
To compare incisal bite force between test adhesives 1 & 2 after 12 hours.	AOB at 12 hours.
Other	
To compare incisal bite force for test adhesive 1 versus no adhesive over 9 hours.	AOB at 0.5, 1, 3, 6 and 9 hours.
To compare incisal bite force for test adhesive 2 versus no adhesive over 9 hours.	AOB at 0.5, 1, 3, 6 and 9 hours.
To compare incisal bite force for test adhesive 1 versus Super Poligrip® Free over 9 hours.	AOB at 0.5, 1, 3, 6 and 9 hours.
To compare incisal bite force for test adhesive 2 versus Super Poligrip® Free over 9 hours.	AOB at 0.5, 1, 3, 6 and 9 hours
To assess subjects' preference with regards to denture adhesive ooze, flavor/	Scores from subject-completed questionnaires on product ooze, at 0.5

Document Name	Statistical Analysis Plan for Study 206233.docx		
Туре	Version	Document Identifier	Effective Date
eldo clinical doc	1.0; CURRENT; Most-Recent; Effective	090032d580d17d34	27-Mar-2017 09:54:18
Reason For Issue	Auto Issue		

after-taste, texture and assess ease of	hours, and flavour/ after-taste, texture and
removal	ease of removal after 12 hours' use
To assess the ease of extrusion of the	Scores from subject-completed
product from the tube by the subjects	questionnaire on product extrusion after
post bite force phase	12 hours' use

3 Study Design

Overall Design

This single centre, randomized, crossover, proof-of-principle study will be a randomized four treatment, examiner blind [to the examiner performing the bite force & oral soft tissue (OST) examinations] design in subjects with well made and moderately well-fitting maxillary complete dentures. Informed consent will be obtained from participants before the implementation of any study procedure.

At the Screening Visit, subjects will be screened for eligibility and ability to perform the bite force manoeuvre according to stated inclusion/exclusion criteria. On the test day visit, subjects will report to the study site without adhesive placed in their dentures. Dentures will be removed and cleaned. An OST examination will be performed before the lower denture (if applicable) is secured using Super Poligrip[®] Flavour Free denture adhesive, whilst the upper denture is removed, and the pretreatment baseline incisal bite force measurements will be obtained (both practice bites and qualifying test bite). To maintain blinding, subjects must not disclose to the examiner if they are wearing adhesive or no adhesive. Subjects meeting all the inclusion criteria with no exclusions will then be randomized at Visit 2.

On each test day (Visits 2-5) subjects will undergo an OST examination and have their dentures cleaned. Denture adhesive treatment (or no treatment as per the randomization schedule) will then be applied by a member of study staff (ideally the same member of staff throughout the study) as per the application instructions, and the dentures worn by the subject. Incisal bite force measurements will be made at 0.5, 1, 3, 6, 9 and 12 hours after the dentures are placed in the mouth. After 0.5 hours assessment the subjects will be asked to complete questions about product ooze (Appendix II). The questions will be completed by the subjects themselves and these responses will then be given to study site staff to transfer to the eCRF.

Immediately following the last (12 hour) incisal bite force measurement, subjects will be asked to complete a short questionnaire relating to the after-taste and texture of the

Document Name	Statistical Analysis Plan for Study 206233.docx		
Туре	Version	Document Identifier	Effective Date
eldo clinical doc	1.0; CURRENT; Most-Recent; Effective	090032d580d17d34	27-Mar-2017 09:54:18
Reason For Issue	Auto Issue		

denture adhesive (Appendix III). This will be completed by the subject themselves in a quiet environment without external influence.

Immediately following subsequent upper denture removal by the subjects themselves, subjects will be asked to answer another short questionnaire (which will be administered by the site staff; Appendix IV) pertaining to ease of removal of the denture when undertaking the treatment phases of the study, but not the negative no treatment control arm. The subjects will remove their dentures by themselves under supervision by site staff. Following denture removal, and completion of the associated questionnaire, site staff will clean the denture before returning to the patient at the end of the study.

These assessments will be followed by the final post-treatment OST examination.

These procedures will be repeated in a crossover manner. There will be at least 24 hours (up to 14 days) between treatment visits to allow recovery from the bite force procedures.

Visit 1 - Screening Visit

The following assessments will be conducted in the order written:

- Written informed consent.
- Demographics, medical history, current/concomitant medications, and dental history.
- Criteria for well made dentures
- Inclusion/exclusion criteria
- Oral soft tissue examination including edentulous maxillary arch
- Denture bearing tissue score
- Kapur Index assessment
- Denture cleansing
- Mandibular denture stabilization (with adhesive, if deemed to be necessary to ensure accurate bite force measures; at the discretion of the Investigator)
- Three incisal bite force readings with no adhesive on upper denture (for training)
- Incisal bite force with no adhesive on the upper denture (qualifying)
- Inclusion/exclusion criteria (following initial bite force measures)
- Subject eligibility
- Adverse events and incident reporting (assessed from the start of the first bite force measurement)

Visits 2, 3, 4 & 5

The following assessments will be conducted:

Document Name	Statistical Analysis Plan for Study 206233.docx		
Туре	Version	Document Identifier	Effective Date
eldo clinical doc	1.0; CURRENT; Most-Recent; Effective	090032d580d17d34	27-Mar-2017 09:54:18
Reason For Issue	Auto Issue		

- Review of current/concomitant medications, adverse events and incidents
- Oral soft tissue examination including edentulous maxillary arch
- Denture cleansing
- Mandibular denture stabilization (with adhesive, if deemed to be necessary to ensure accurate bite force measures; at the discretion of the Investigator)
- Three incisal bite force readings with no adhesive on the upper denture (for practice)
- Incisal bite force with no adhesive on the upper denture (pre-treatment "baseline")
- Subject eligibility
- Adverse events and incident reporting (assessed pre bite force measurement)
- Continued eligibility
- Randomisation (Test/Treatment day 1 only)
- Weigh maxillary denture prior to adhesive placement
- Product application by site staff to maxillary denture (or no adhesive for the no adhesive negative control)
- Weigh maxillary denture immediately following adhesive placement (record weight difference i.e. weight of adhesive used to ensure correct dose applied)
- Dentures of subjects randomized to a denture adhesive shall be weighed before & after adhesive application
- Upper denture insertion by subject
- Incisal bite force measurements (at 0.5 hours prior to product ooze questionnaire (Appendix II), followed by 1, 3, 6, 9 & 12 hours post adhesive application)
- Subject evaluation questionnaire (product ooze) 0.5 hours post adhesive application (Appendix II)
- Subject sensory questionnaire (flavour, texture and extrusion of the adhesive from the tube; Appendix III) immediately following the last (12 hr) bite force measure whilst upper denture still retained in the mouth
- Removal of denture from the mouth by the subject
- Denture adhesive retention questionnaire completed by Examiner/ site staff
- Removal of excess adhesive from the mouth by the subject facilitated by site study staff as and where necessary
- Subject denture removal questionnaire (Appendix IV) immediately following 12 hour post adhesive application bite force measure, completion of subject sensory questionnaire and subsequent removal of the upper denture
- Study Staff to check denture removal questionnaire completion to ensure that
 any potential AEs which may have been noted in the questionnaire free text is
 reviewed and captured in the eCRF before the subject leaves the site

Document Name	Statistical Analysis Plan for Study 206233.docx		
Туре	Version	Document Identifier	Effective Date
eldo clinical doc	1.0; CURRENT; Most-Recent; Effective	090032d580d17d34	27-Mar-2017 09:54:18
Reason For Issue	Auto Issue		

- Post-treatment OST by a blinded examiner
- · Dentures cleaned and returned to subject
- Adverse events and incident reporting (assessed post bite force measurement)

There will be at least 24 hours (up to 14 days) between subsequent treatment days to allow recovery from the bite force procedures.

